10.6.8 COVID-19 Impacted Visits

A listing containing subjects' visits impacted due to COVID-19 will be provided.

11 LIST OF APPENDICES

Appendix A Analysis Visit Windows for Safety and Pharmacodynamic Assessments

Table 11-1 Visit Window Mapping Rules for Rollover Subjects (809-124)

Assessments	Visit	Target Study Day	Visit Window (in study days)
Weight and	Day 15	15	(1, 50]
length/height	Week 12	85	[51, 127]
 Vital signs 	Week 24	169	[128, 211]
 Pulse oximetry 	Week 36	253	[212, 295]
• Labs	Week 48	337	[296, 379]
 LFTs Only 	Week 60	421	[380, 463]
	Week 72	505	[464, 547]
	Week 84	589	[548, 631]
	Week 96	673	[632, 680]
	Follow-up Visit	687	Nominal Visit
• IRT	Week 12	85	(1, 127]
• Labs	Week 24	169	[128, 211]
 Chemistry 	Week 36	253	[212, 295]
 Hematology 	Week 48	337	[296, 379]
	Week 60	421	[380, 463]
	Week 72	505	[464, 547]
	Week 84	589	[548, 631]
	Week 96	673	[632, 680]
	Follow-up Visit	687	Nominal Visit
• Standard 12-Lead ECG	Week 24	169	(1, 253]
• Sweat chloride	Week 48	337	[254, 505]
• Fecal Sample	Week 96	673	[506, 680]
Fecal CalprotectinFecal Elastase-1	Follow-up Visit	687	Nominal Visit
Ophthalmological	Week 24	169	(1, 253]
Examination	Week 48	337	[254, 421]
	Week 72	505	[422, 589]
	Week 96	673	[590, 680]
	Follow-up Visit	687	Nominal Visit

If ETT visit happens on or after 10 days of last LUM/IVA dose and there are no SFU assessments collected, then ETT Visit will be mapped to SFU analysis Visit.

Table 11-2 Visits Window Mapping Rules for LUM/IVA-naïve Subjects (809-124)

Assessments	Visit	Target Study Day	Visit Window (in study days)
Weight and	Day 15	15	(1, 22]
length/height	Week 4	29	[23, 43]
 Vital signs 	Week 8	57	[44, 71]
Pulse oximetry	Week 12	85	[72, 99]
• Labs	Week 16	113	[100, 141]
 LFTs Only 	Week 24	169	[142, 211]
•	Week 36	253	[212, 295]
	Week 48	337	[296, 379]
	Week 60	421	[380, 463]
	Week 72	505	[464, 547]
	Week 84	589	[548, 631]
	Week 96	673	[632, 680]
	Follow-up Visit	687	Nominal Visit
Standard 12-Lead ECG	Week 4	29	(1, 57]
	Week 12	85	[58, 127]
	Week 24	169	[128, 253]
	Week 48	337	[254, 505]
	Week 96	673	[506, 680]
	Follow-up Visit	687	Nominal Visit
• Labs	Week 4	29	[23, 43]
 Chemistry 	Week 8	57	[44, 71]
 Hematology 	Week 12	85	[72, 99]
- 67	Week 16	113	[100, 141]
	Week 24	169	[142, 211]
	Week 36	253	[212, 295]
	Week 48	337	[296, 379]
	Week 60	421	[380, 463]
	Week 72	505	[464, 547]
	Week 84	589	[548, 631]
	Week 96	673	[632, 680]
	Follow-up Visit	687	Nominal Visit
• IRT	Week 4	29	(1, 57]
	Week 12	85	[58, 127]
	Week 24	169	[128, 211]
	Week 36	253	[212, 295]
	Week 48	337	[296, 379]
	Week 60	421	[380, 463]
	Week 72	505	[464, 547]
	Week 84	589	[548, 631]
	Week 96	673	[632, 680]
	Follow-up Visit	687	Nominal Visit

Sweat chloride	Week 4	29	(1, 57]
 Fecal Sample 	Week 12	85	[58, 127]
1	Week 24	169	[128, 253]
	Week 48	337	[254, 505]
	Week 96	673	[506, 680]
	Follow-up Visit	687	Nominal Visit
Ophthalmological	Week 24	169	(1, 253]
Examination	Week 48	337	[254, 421]
	Week 72	505	[422, 589]
	Week 96	673	[590, 680]
	Follow-up Visit	687	Nominal Visit

The study days are based on the first dose in Study 124.

For Vital signs the Nominal Day 15 predose assessments will be mapped to Day 15.

Appendix B Imputation Rules for Missing Prior/Concomitant Medication Dates

Imputation rules for missing or partial medication start/stop dates are defined below:

- 1. Missing or partial medication start date:
 - a. If only DAY is missing, use the first day of the month.
 - b. If DAY and Month are both missing, use the first day of the year.
 - c. If DAY, Month and Year are all missing, use the informed consent date.
- 2. Missing or partial medication stop date:
 - a. If only DAY is missing, use the last day of the month.
 - b. If DAY and Month are both missing, use the last day of the year.
 - c. If DAY, Month and year are all missing, assign 'continuing' status to stop date (in practice, use the end of study date to impute).

In summary, the prior, concomitant or post categorization of a medication is described below.

Table 11-3 Prior, Concomitant, and Post Categorization of a Medication

	Medication Stop Date		
Medication Start Date	< First Dose Date of Study Drug	≥ First Dose Date and ≤ End Date of TE Period	> End Date of TE Period
< First dose date of study drug	P	PC	PCA
≥ First dose date and ≤ End date of TE period	-	С	CA
> End date ofTE period	-	-	A

A: Post; C: Concomitant; P: Prior; TE: treatment-emergent

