#### 3 SCHEDULE OF ASSESSMENTS

Schedules of assessments are in Table 3-1 and Table 3-2.

Table 3-1 Study VX19-809-124: Rollover Subjects

	Treatment Period (Day 1 Through Week 96)						SFU Visit °	Follow-up OE	
Event/ Assessment a	Day 1 d	Day 3 (± 1 Day)	Day 15 (± 3 Days)	Weeks 12, 24, 36, 48, 60, 72, and 84 (± 7 Days)	Week 96 (± 7 Days)	As Soon As Possible After Last Dose	2 Weeks (±4 Days) After Last Dose	24 Weeks (± 14 Days ) After Last Dose	Comments
Informed consent	X								
Inclusion/exclusion criteria confirmation	X								
Telephone contact		X							Assessment of subject's status, any AEs, concomitant medications, treatments, and procedures.
Clinic visit	X		X	X	X	X	X		See Section 9.1.6 for use of remote measures in extenuating circumstances.
Length/height and weight	X		X	X	X	X	X		Measured with the subject in a dry diaper or dry underclothes. If the subject is >2 years of age and can stand unassisted and follow directions, standing height should be measured; otherwise recumbent length should be measured. (Section 11.3.1).
Vital signs	X		X	X	X	X	X		The subject should rest for at least 5 minutes, if possible, before having vital signs measured. (Section 11.4.4)
Pulse oximetry	X		X	X	X	X	X		The subject should rest for at least 5 minutes, if possible, before having pulse oximetry measured. (Section 11.4.4)

<sup>a Assessments will be performed before dosing unless noted otherwise.

b If the ETT Visit occurs ≥10 days after the last dose of LUM/IVA, SFU Visit will not be required (Section 9.1.4). Subjects who prematurely discontinue LUM/IVA treatment for AEs should be followed until the AE is considered resolved.

The SFU Visit is required for 1) subjects who complete their ETT Visit <10 days after the last dose of LUM/IVA (footnote b and Section 9.1.4); and 2) subjects who interrupt LUM/IVA treatment and complete their Week 96 Visit <10 days after the last dose of LUM/IVA; it is not required for subjects who continue onto commercially available, physician-prescribed LUM/IVA within 2 weeks (± 4 days) of completing LUM/IVA treatment at the Week 96 or ETT Visit.

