# 9.1.1 Screening (LUM/IVA-naïve Subjects Only)

Screening Visit assessments are listed in Table 3-2.

Screening will occur within 28 days before administration of LUM/IVA. The investigator (or an appropriate authorized designee at the study site) will obtain informed consent from each subject's parent or legal guardian.

To prepare for study participation, subject's parent or legal guardian will be instructed on the study restrictions (Section 9.4).

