#### 9.1.2 Treatment Period

Treatment Period assessments are listed in Table 3-1 for Rollover Subjects and Error! Reference source not found. for LUM/IVA-naïve Subjects. Subjects will be outpatients during the Treatment Period. All visits and telephone contacts should occur within the windows specified.

The Treatment Period is 96 weeks; LUM/IVA will be administered every 12 hours (q12h) from Day 1 up to Week 96. LUM/IVA dose and administration details are provided in Section 9.6.

Procedures for subjects who prematurely discontinue LUM/IVA treatment are described in Section 9.1.4.

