#### 9.5 Prior and Concomitant Medications

Information regarding all prior and concomitant medications, including the subject's CF medications, other medications, and herbal and naturopathic remedies administered from 28 days before the first dose through the Safety Follow-up Visit, if applicable, will be recorded in each subject's source documents. In addition, concomitant medication dose(s) may be collected.

- It is recommended that subjects remain on a stable medication regimen for their CF from 28 days before Day 1 through the Safety Follow-up Visit, if applicable. Stable medication regimen is defined as the current medication regimen for CF that subjects have been following for at least 28 days before Day 1. Note: PERT doses may be adjusted during this study.
- While the etiology of respiratory events associated with LUM/IVA is not yet known, data from healthy subjects in Study 009 Cohort 4 suggest that treatment with short-acting

bronchodilators may reverse the initial transient decline in percent predicted forced expiratory volume in 1 second (ppFEV1) when dosed with LUM/IVA. Subjects may be prescribed a short-acting bronchodilator in accordance with local drug labeling (if not already prescribed) to ensure constant availability during the study.

• Information about bronchodilator use during the study will be collected and documented in the subject's source documents.

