10.2.3 Prior and Concomitant Medications

Medications used will be coded using the World Health Organization Drug Dictionary (WHODrug) and categorized as the following:

Prior medication: Any medication that started before the date of the first dose of study drug in Study 124.

Concomitant medication: Any medication continued or newly received during the TE Period.

Post-treatment medication: Any medication continued or newly received after the end of the TE Period.

A given medication can be classified as prior; concomitant; post-treatment; both prior and concomitant; both concomitant and post-treatment; prior, concomitant, and post-treatment.

Prior medications and concomitant medications will be summarized descriptively using frequency tables by preferred name and by ATC level 1 and 2 based on Safety Set.

All medications will be listed for each subject.

Details for imputing missing or partial start and/or stop dates of medication are described in Appendix.

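### An unknown medication start date is set to consent, which for Rollover Subjects consenting on Day 1 is the first-dose date, so medication already in use is not counted as prior

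*SAP*

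**What the plan says.** SAP Appendix B imputes missing medication start dates in three steps. A missing day becomes the first of the month (1a). A missing day and month become the first of the year (1b). For a wholly missing date, rule 1c reads: "If DAY, Month and Year are all missing, use the informed consent date". The rule does not name the study whose consent is meant, and it does not compare the imputed start with the stop date.

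SAP 10.2.3 defines prior medication as "Any medication that started before the date of the first dose of study drug in Study 124", and Protocol 12.3.2.3 agrees. Table 11-3 in Appendix B then assigns each record to prior (P), concomitant (C), post-treatment (A) or a combination, according to where its start and stop dates fall. Three combinations of start and stop hold only a dash.

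In Protocol Table 3-1 (Rollover Subjects) the row "Informed consent" is marked at Day 1 only, and the table has no screening column. Table 3-2 (LUM/IVA-naïve Subjects) marks consent at screening, Days -28 through -1. On dosing, Protocol 9.1.2 states: "LUM/IVA will be administered every 12 hours (q12h) from Day 1 up to Week 96". Protocol 9.5 records medications "administered from 28 days before the first dose through the Safety Follow-up Visit", so treatments that ended before the first dose can be in the data.

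**The concern.** The same fallback date means different things in the two cohorts. For naïve Subjects, consent comes before the first dose. For Rollover Subjects on the scheduled timing it is the first-dose date itself, and a start on that date does not meet the definition of prior.

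Two kinds of Rollover record are affected. An undated medication still in use at first dose drops out of the prior-medication table but stays in the concomitant table. An undated medication that stopped before first dose gets no category from Table 11-3, although anything that stopped before first dose must also have started before it.

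Protocol Version 2.0 revised the prior-medication definition so that medications taken during Study 122 would be captured for Rollover Subjects. For records without a start year, rule 1c works against that aim.

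**Working it through.** The plan states no figure to reproduce. The check traces rule 1c through Table 11-3.

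**Inputs**

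- Imputed start = informed consent date (SAP Appendix B, rule 1c).
- Consent: Day 1 for Rollover Subjects (Protocol Table 3-1); Days -28 through -1 for naïve Subjects (Table 3-2).
- First dose on Day 1 (Protocol 9.1.2). SAP Appendix A counts from the same point: "The study days are based on the first dose in Study 124".
- Table 11-3 row for a start before first dose: P, PC or PCA, by stop date.
- Table 11-3 row for a start from the first dose to the end of the treatment-emergent (TE) period: a dash if the stop is before first dose; C if the stop falls in the column "≥ First Dose Date and ≤ End Date of TE Period"; CA if the stop is later.

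**Set-up**

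Days are counted from the first dose, with the first-dose date as 0. For illustration, the TE period ends at 672 + 18 = 690, where 672 = 673 - 1 (Week 96 target study day less 1) and 18 days is the tail in SAP section 9. The result does not depend on this value. Stop dates tested: each of the 28 days from -28 to -1, then 0, 100 and 690 (within the TE period), then 691 and 800 (after it), 33 in all.

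**Results**

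| Case | 28 stops before first dose | 3 stops in TE period | 2 stops after TE period | Stops earlier than imputed start |
|---|---|---|---|---|
| Rollover, consent on first-dose date (0) | dash: 28 | C: 3 | CA: 2 | 28 |
| Rollover, consent one day earlier (-1) | P: 28 | PC: 3 | PCA: 2 | 27 |
| Naïve, consent at -1 | P: 28 | PC: 3 | PCA: 2 | 27 |
| Naïve, consent at -28 | P: 28 | PC: 3 | PCA: 2 | 0 |

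In the first case no stop date leads to P, PC or PCA. A wholly missing stop date, which Appendix B sets to the end of study, gives C or CA. In the other three cases every record counts as prior. The last column shows a second defect: with consent shortly before first dose, the category is right but the imputed start can still fall after the recorded stop.

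**Comparison with the adverse event rule**

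For an adverse event with no start year, SAP Appendix C compares the end date with the first dose and calls the event pretreatment if it ended earlier. Appendix B has no matching step for medications.

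**The case against.** Several points on the other side stand and set the limits of this one.

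- **A reader might infer that an undated Rollover medication can never be prior.** The documents do not support that. It requires the Study 124 consent, signed on the first-dose date. Table 3-1 is a visit schedule, Protocol 9.1.6 allows remote consent, and some Rollover Subjects need medical-monitor approval before entry or before resuming drug. Consent one day earlier, or a first dose after the Day 1 Visit, makes the record prior. So would reading rule 1c as the Study 122B consent, although Study 124 is the natural reading.
- **A reader might infer that less information always gives a later start.** That is false between rules 1a and 1b, where losing the month as well as the day moves the start earlier. Only the step to 1c departs from imputing to the start of the known period.
- **A reader might infer a distorted comparison of Rollover with naïve Subjects.** The plan summarises medications on the pooled Safety Set and plans no such comparison. What remains is one pooled table that applies the rule unevenly.
- **A reader might infer that the Version 2.0 change is undone.** Complete dates are unaffected and partial dates generally remain prior. Protocol 13.3 has missing data queried, so rule 1c meets only what is left.

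It can also be said that Table 11-3 only summarises the definitions, that a medication stopped before first dose is prior by definition whatever the table shows, and that every medication is listed anyway. This is fair, but it confirms that the imputed date and the definition disagree. A program that follows the imputed date and the table would leave the record out of the prior-medication summary.

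**Conclusion.** The point holds as a minor error in a stated rule. When Study 124 consent is signed on the first-dose date, as scheduled, a Rollover medication with a wholly missing start is classed C or CA. If it stopped before first dose it falls in a dash cell, although SAP 10.2.3 makes it prior. The same record in a naïve Subject is P, PC or PCA.

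The effect is confined to descriptive medication summaries; no primary, secondary or exploratory endpoint is touched. Its size cannot be computed, because the documents do not say how many medication records lack a start year. The number may be zero, and the documents give no upper bound.

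**What to change.** Replace rule 1c in SAP Appendix B with: if the medication start date is completely missing, use the earliest of the Study 124 informed consent date, the day before the first Study 124 dose, and the stop date (observed or imputed).

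The imputed start is then always before the first dose, so every such record in either cohort becomes P, PC or PCA. It is also never later than the stop date, so no undated record reaches a dash cell or has its dates reversed. Any medication stopped before first dose becomes prior, which matches the end-date check in Appendix C. Naming Study 124 settles which consent is meant.

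The change is one sentence plus the matching program line. The downside is small: an undated medication that in fact began on study is also shown as prior, as rule 1c already does for naïve Subjects.

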Appendix C Imputation Rules for Missing AE dates

Imputation rules for missing or partial AE start date are defined below:

If only Day of AE start date is missing:

If the AE start year and month are the same as that for the first dose date, then:

- If the full (or partial) AE end date is NOT before the first dose date or AE end date is missing, then impute the AE start day as the day of first dose date; otherwise, impute the AE start day as 1.
- Otherwise, impute the AE start day as 1.

Compare the imputed AE start date with Treatment-Emergent period to determine whether the AE is pretreatment AE, TEAE or post-treatment AE.

If Day and Month of AE start date are missing:

If AE start year = first dose year, then:

- If the full (or partial) AE end date is NOT before the first dose date or AE end date is missing, then impute the AE start Month and Day as the Month and Day of first dose date; otherwise, impute the AE start Month as January and the Day as 1.
- Otherwise, impute the AE start MONTH as January and the DAY as 1.

Compare the imputed AE start date with Treatment-Emergent period to determine whether the AE is pretreatment AE, TEAE or post-treatment AE.

If Year of AE start date is missing:

If the year of AE start is missing or AE start date is completely missing, then query site with no imputation. Also compare the full (or partial) AE end date to the first dose date. If the AE end date is before the first dose date, then the AE should be considered as a pretreatment AE. Otherwise, the AE will be considered as TEAE.

Appendix D Criteria for Threshold Analysis

Table 11-4 Threshold Analysis Criteria for Laboratory Tests

Parameter	Categorical change	Comments			
Clinical Chemistry	Clinical Chemistry				
ALT	≤3xULN*(Not a categorical change) >3x - ≤ 5xULN >5x - ≤ 8xULN >3xULN >5xULN >5xULN >8xULN	FDA DILI Guidance Jul 2009.			
AST	≤3xULN*(Not a categorical change) >3x - ≤ 5xULN >5x - ≤ 8xULN >3xULN >5xULN >8xULN	FDA DILI Guidance Jul 2009.			
ALT or AST	ALT>3xULN or AST>3xULN	Vertex LFT working group 2014			
ALT or AST	ALT>5xULN or AST>5xULN				
ALT or AST	ALT>8xULN or AST>8xULN				
Alkaline Phosphatase	>1.5xULN	FDA DILI Guidance Jul 2009.			
Total Bilirubin	>1.5x - ≤2xULN >2xULN	FDA DILI Guidance Jul 2009.			
ALT and Total Bilirubin	ALT>3xULN and TBILI>2xULN	FDA DILI Guidance Jul 2009. To be counted within a same treatment phase, whatever the interval between measurements.			
AST and Total Bilirubin	AST>3xULN and TBILI>2xULN	FDA DILI Guidance Jul 2009. To be counted within a same treatment phase, whatever the interval between measurements.			
(ALT or AST) and Total Bilirubin	(ALT>3xULN or AST>3xULN) and TBILI>2×ULN	Vertex LFT working group 2014			
СРК	$>3x - \le 10xULN$ >10xULN	FDA criteria Feb 2005. Am J Cardiol April 2006.			
Creatinine	≥150 µmol/L (Adults) ≥30% change from baseline ≥100% change from baseline	Benichou C., 1994.			
Blood Urea Nitrogen	≥17 mmol/L				
Sodium	≤129 mmol/L ≥150 mmol/L				
Potassium	<3 mmol/L ≥5.5 mmol/L	FDA Feb 2005.			

Parameter	Categorical change	Comments
Glucose		
Hypoglycaemia Hyperglycaemia	≤3.9 mmol/L and <lln ≥11.1 mmol/L (unfasted); ≥7 mmol/L (fasted)</lln 	ADA May 2005. ADA Jan 2008.
Albumin	≤25 g/L	
Hematology		
WBC	<3.0 Giga/L (Non-Black); <2.0 Giga/L (Black) ≥16.0 Giga/L	Increase in WBC: not relevant. To be interpreted only if no differential count available.
Lymphocytes	>4.0 Giga/L	
Neutrophils	<1.5 Giga/L (Non-Black); <1.0 Giga/L (Black)	International Consensus meeting on drug- induced blood cytopenias, 1991. FDA criteria.
Monocytes	>0.7 Giga/L	
Basophils	>0.1 Giga/L	
Eosinophils	>0.5 Giga/L or >ULN (if ULN≥0.5 Giga/L)	Harrison- Principles of internal Medicine 17th Ed., 2008.
Hemoglobin	≤115 g/L (Male); ≤95 g/L (Female) ≥185 g/L (Male); ≥165 g/L (Female) Decrease from Baseline ≥20 g/L	Criteria based upon decrease from baseline are more relevant than based on absolute value. Other categories for decrease from baseline can be used (\geq 30 g/L, \geq 40 g/L, \geq 50 g/L).
Platelets	<100 Giga/L ≥700 Giga/L	International Consensus meeting on drug- induced blood cytopenias, 1991.

Table 10-5 Threshold Analysis Criteria for ECGs

Parameter	Categorical change	Comments
HR	≤70 bpm	
	≥150 bpm	
PR		
	≥150 ms	
QRS	≥80 ms	
QTc	Absolute values (ms)	To be applied to any kind of QT correction formula.
	Prolonged: >450 ms (Male and Female)	

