#### 8.2 LUM/IVA-naïve Subjects

#### 8.2.1 Inclusion Criteria

- 1. Subject's legally appointed and authorized representative (e.g., parent or legal guardian) will sign and date an informed consent form (ICF).
- 2. As deemed by the investigator, the subject's legally appointed and authorized representative (e.g., parent or legal guardian) must be able to understand protocol requirements, restrictions, and instructions. The subject's legally appointed and authorized representative should be able to ensure that the subject will comply with, and is likely to complete, the study as planned.
- 3. Subjects (male and female) will be 12 to <24 months of age on Day 1.
- 4. Weight at screening must be within the weight limits as defined for the study drug dose levels (see Section 9.6) or according to the dosing guidelines identified in the "Justification for Dose Selection" memorandum effective at the time a subject is screened.

- 5. Subjects with confirmed diagnosis of CF at screening. CF is defined as:
  - 2 CF-causing mutations (all as documented in the subject's medical record)
    - O Subjects must be homozygous for *F508del* (genotype to be confirmed at screening): If a genotype test has been performed previously and is documented in the subject's medical record, the subject is not required to be tested for *CFTR* genotype at screening, but the subject's eligibility must be approved by the Vertex medical monitor. If a historic genotype result is not available at screening or if the historic genotype result is not approved by the Vertex medical monitor, the subject will be tested for *CFTR* genotype at screening, and the results must be reviewed before the first dose. Note: Newborn screening genotype results are not sufficient for eligibility.

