#### 8.2.2 Exclusion Criteria

- 1. History of any comorbidity reviewed at screening that, in the opinion of the investigator, might confound the results of the study or pose an additional risk in administering LUM/IVA to the subject. For example, a history of cirrhosis with portal hypertension.
- 2. Any clinically significant laboratory abnormalities at screening that would interfere with the study assessments or pose an undue risk for the subject (as deemed by the investigator).
- 3. Any of the following abnormal laboratory values at screening:
  - Hemoglobin < 9.5 g/dL
  - Alanine aminotransferase (ALT), aspartate aminotransferase (AST), or total bilirubin >2 × upper limit of normal (ULN)
  - Chronic kidney disease of Stage 3 (estimated glomerular filtration rate [eGFR] <60 mL/min/1.73 m^2 calculated by the Bedside Schwartz equation) based on the normal range for eGFR in this age group (62 to 191)
- 4. An acute upper or lower respiratory infection, pulmonary exacerbation (PEx), or changes in therapy (including antibiotics) for pulmonary disease within 28 days before Day 1 (first dose of LUM/IVA).

- 5. A standard 12-lead ECG demonstrating QTc >450 msec at screening. If QTc exceeds 450 msec at the Screening Visit, the ECG should be repeated 2 more times during the Screening Period, and the average of the 3 QTc values should be used to determine the subject's eligibility.
- 6. History of solid organ or hematological transplantation.
- 7. Ongoing or prior participation in an investigational drug study (including studies investigating LUM and/or IVA) within 30 days of screening.
  - A washout period of 5 terminal half-lives of the previous investigational study drug, or 30 days, whichever is longer, must elapse before the Screening Visit.
  - The duration of the elapsed time may be longer if required by local regulations.

Note: Ongoing participation in a noninterventional study (including observational studies) is permitted.

[figure not shown]
- 8. Use of restricted medication or food within specified duration before the first dose of LUM/IVA as defined in Section 9.4.
- 9. An adequate slit-lamp examination could not be conducted at the Screening OE.

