7 STUDY DESIGN

7.1 Overall Design

This is a Phase 3, multicenter, open-label study in subjects who are 12 to <24 months of age at initiation of LUM/IVA treatment (

Figure 7-1). The study will enroll approximately 50 subjects.

Rollover Subjects

Subjects who participated in parent study VX16-809-122 Part B (Study 122B) and meet all eligibility requirements can rollover into Study 124.

For rollover subjects at sites activated by the Study 122B Safety Follow-up (SFU) Visit, their Study 124 Day 1 Visit will be on the same day as their Study 122B SFU Visit; any Study 124 Day 1 assessments that are specified to be performed at the Study 122B SFU Visit will not need to be repeated.

If the Study 124 Day 1 Visit does not coincide with the Study 122B SFU Visit, and if Study 124 Day 1 is \leq 9 days after the Study 122B SFU Visit, the Study 124 Day 1 assessments will not need to be repeated. Otherwise, if Study 124 Day 1 is >9 days after the Study 122B SFU Visit, the subject will need to complete all Study 124 Day 1 assessments (except the OE if it was performed \leq 12 weeks before the Study 124 Day 1 Visit).

Rollover subjects may receive treatment for up to 120 weeks (24 weeks in Study 122B and 96 weeks in Study 124).

LUM/IVA-naïve Subjects

[figure not shown]
Subjects who did not participate in Study 122B and are 12 to <24 months of age at Study 124 Day 1 can enroll by age group if they meet Study 124 eligibility requirements:

- Subjects who are 18 to <24 months of age can enroll in Study 124 after a minimum of 10 subjects (aged 18 to <24 months) have enrolled in Study 122B and after an assessment of safety data from Study 122B through Week 12 for ≥5 subjects aged 18 to <24 months.
- Subjects who are 12 to <18 months of age can enroll in Study 124 after a minimum of 10 subjects (aged 12 to <18 months) have enrolled in Study 122B and after an assessment of safety data from Study 122B through Week 12 for ≥5 subjects aged 12 to <18 months.

Note: Subjects aged 18 to <24 months will start enrolling in Study 124 before any subjects 12 to <18 months of age can enroll as a result of the staggered timing from the Study 122 study design, which includes sequential age cohorts.

LUM/IVA-naïve subjects may receive treatment for up to 96 weeks in Study 124.

Figure 7-1 Schematic of Study 124 Design

IVA: ivacaftor; LUM: lumacaftor; OE: ophthalmological examination; q12h: every 12 hours; wks: weeks

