10 STATISTICAL ANALYSIS

10.1 General Considerations

The Schedule of Assessments is provided in the CSP for Study 124. The precision standards for reporting safety and efficacy variables are provided in an internal Biometrics document that specifies the programming rules including the precision for derived variables.

All individual subject data will be presented in data listings based on the All Subjects Set.

Continuous variables will be summarized using the following descriptive summary statistics: number of subjects, mean, standard deviation (SD), standard error (SE), median, minimum value (min), and maximum value (max).

Categorical variables will be summarized using counts and percentages.

Baseline value will be defined as the most recent non-missing measurement (scheduled or unscheduled) collected on or before the first dose of LUM/IVA in Study 124.

For sweat chloride, values at each visit will be based on averaged measurements from left and right arms. For Rollover Subjects, baseline will be defined as the most recent non-missing measurement (scheduled or unscheduled) collected on or before the first dose of LUM/IVA in Study 124. For LUM/IVA-naïve Subjects, baseline will be defined as the average of the values at screening and the pretreatment measurement on Day 1 of Study 124. If only 1 pre-first dose measurement of sweat chloride is available, that measurement will be considered the baseline.

Change (Absolute Change) from baseline will be calculated as postbaseline value – baseline value.

Unscheduled visits will be included in the analysis as follows:

- In scheduled visit windows per specified visit windowing rules
- In the derivation of baseline measurements or last on-treatment visit
- In individual subject data listings, as appropriate
- In the derivation of max/min values and max/min change from baseline values

Visit windowing rules: Appendix defines the visit window mapping rules to derive the analysis visits for Study 124.

Repeated observations within the same visits window:

- For all PD parameters, if there are multiple measurements within a visit window, the record at the scheduled visit will be used. If there are no measurements at the scheduled visit, then 1) the record closest to the target day will be used; or 2) if there are multiple records with the same distance to the target day, the latest record will be used.

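### SAP Table 11-4 has no absolute creatinine limit usable in toddlers, and its ≥30% creatinine row cannot separate growth plus ordinary variability from a loss of kidney function

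*SAP*

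**What the plan says.** The creatinine row of Table 11-4 (SAP Appendix D) holds three criteria: an absolute one, "≥150 µmol/L (Adults" being its wording up to the closing bracket, and two relative ones, "≥30% change from baseline ≥100% change from baseline". The relative criteria carry no direction word. The hemoglobin row of the same table does: "Decrease from Baseline ≥20 g/L".

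SAP 10.1 defines change with a sign: "Change (Absolute Change) from baseline will be calculated as postbaseline value – baseline value". It does not define percent change. Baseline is a single value, the "most recent non-missing measurement (scheduled or unscheduled) collected on or before the first dose of LUM/IVA in Study 124". SAP 10.6.2 counts threshold criteria over the treatment-emergent period, which SAP section 9 runs to 18 days after the last dose.

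On age, Protocol 8.2.1 requires of LUM/IVA-naïve subjects: "Subjects (male and female) will be 12 to <24 months of age on Day 1". Rollover subjects also began LUM/IVA in that age range, and SAP 7.1 adds: "Rollover subjects may receive treatment for up to 120 weeks (24 weeks in Study 122B and 96 weeks in Study 124" is the wording, again up to the closing bracket.

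For entry of naïve subjects, Protocol 8.2.2 judges kidney function by eGFR, "calculated by the Bedside Schwartz equation", excludes values below 60 mL/min/1.73 m² and cites an age-group normal range of 62 to 191. No eGFR criterion appears in Table 11-4. By contrast, SAP 10.6.4 adjusts the blood pressure counts for sex, age and length/height.

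**The concern.** A threshold table should give counts that a reader can interpret directly. Here the one absolute creatinine criterion is written for a population that the study does not enrol. The main relative criterion has a fixed reference point while the children grow for almost two years. If creatinine rises with body length at constant kidney function, which is how a length-based eGFR treats it, part of the 30% margin is used up by growth and ordinary variability can carry a child across.

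Laboratory safety is part of the primary endpoint and there is no control arm. A high percentage in the ≥30% row would therefore have no comparator to show how much of it is growth. With no working absolute limit in the same row, the reader also could not see whether flagged children had reached a level of concern.

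**Working it through.** The plan states no figure to reproduce: there is no sample size calculation and no hypothesis test, and the documents contain no creatinine, growth or variability data. Four checks were made.

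**1. Can the adult limit apply to anyone?** Treatment lasts 96 × 7 = 672 days, and 672/30.4375 = 22.1 months (22.7 with the 18-day tail).
- Naïve subjects end treatment at 12 + 22.1 = 34 to 24 + 22.1 = 46 months.
- Rollover subjects enter about 26 weeks (6.0 months) after starting, assuming 24 weeks of treatment plus about 2 weeks to the Safety Follow-up Visit. They end at about 40 to 52 months.

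The limit therefore applies to 0 of about 50. Applying it regardless would not help. The protocol names the Bedside Schwartz equation without printing it; assume eGFR = k × length(cm)/(creatinine in µmol/L ÷ 88.4) with k = 0.413. Then 150 µmol/L is an eGFR of 18.3 at 75 cm and 20.7 at 85 cm, whereas eGFR 60 corresponds to 45.6 and 51.7 µmol/L. For k from 0.35 to 0.55, 150 µmol/L is an eGFR of 15.5 to 27.6 over those lengths.

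**2. What does growth alone do?** At constant eGFR, creatinine ratio = length ratio; k cancels. With assumed baseline length 72–90 cm and gain 12–25 cm, the rise runs from 12/90 = 13.3% to 25/72 = 34.7%. A mid-range case is 18/80 = 22.5%. Reaching 30% from 75 cm needs 22.5 cm. Growth alone therefore crosses 30% only at the top of the range.

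**3. Growth plus variability.** Assumptions: lognormal within-child error with the same CV at baseline and at each draw, and length rising linearly to a total gain G at Week 96. For a single Week 96 draw,

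P(ratio ≥ 1.30) = 1 − Φ( ln[1.30/(1+G)] / (s√2) ), where s = √ln(1+CV²).

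At CV 10%, s = 0.0998 and s√2 = 0.1411. With G = 0, z = 0.2624/0.1411 = 1.86 and P = 0.03. With G = 20%, z = 0.0800/0.1411 = 0.57 and P = 0.29.

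Over the 8 rollover chemistry draws (Weeks 12 to 96, every 12 weeks), all sharing one baseline, simulation gives the expected number of 50 children flagged at least once for a rise of ≥30% with true eGFR unchanged:

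| Length gain | CV 5% | CV 10% | CV 15% |
|---|---|---|---|
| 0 | 0.0 | 7.5 | 19.3 |
| 15% | 3.7 | 20.0 | 29.2 |
| 20% | 10.0 | 25.6 | 32.6 |
| 25% | 20.0 | 31.2 | 35.6 |

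The 9-draw naïve schedule gives nearly the same counts (at 20% gain: 10.0, 25.7, 32.8).

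**4. Direction and the ≥100% row.** For rollover subjects with 15–25% gain, counting falls as well as rises adds at most 0.01 to the per-child probability at CV 10%, and 0.07 to 0.10 at CV 15%. The probability of any ≥100% rise is 0.034 or less at gains up to 25%, on either schedule.

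**The case against.** The strongest reply is that kidney safety does not rest on this row. Table 11-4 also has the ≥100% creatinine criterion, which growth barely touches, and blood urea nitrogen ≥17 mmol/L. SAP 10.6.2 adds raw and change summaries, counts below LLN and above ULN at each visit, and out-of-range listings that include unscheduled visits. Protocol 13.1.1.2 has clinically significant worsening recorded as an adverse event. The study is descriptive, and an unusable adult limit produces no false counts. All of this stands, and it confines the point to how one row reads.

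Three stronger readings might be inferred, and the documents do not support them.

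- *That normal growth by itself trips the 30% row.* No growth or creatinine data are given, and under the assumptions above growth alone mostly stays below 30%. At CV 15%, 19 of 50 would be flagged with no growth at all.
- *That falls are meant to be counted.* The row is silent, but the signed definition in SAP 10.1 favours an increase, and creatinine cannot realistically fall by 100%. Only the wording is at issue.
- *That leaving eGFR out on treatment contradicts the protocol.* eGFR is a screening criterion for naïve subjects only. It is not in the rollover criteria and is not a planned on-treatment measure.

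It is also fair to say that the size depends on inputs from outside the documents. That is why only a range is given.

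**Conclusion.** The point holds in limited form. Two things follow from the text alone: the threshold analysis has no absolute creatinine limit that can apply to any subject, and the ≥30% row has no stated direction, one fixed baseline and no length or age adjustment over about 22 months.

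The size is conditional. If creatinine is proportional to length at constant eGFR, with 15–25% length gain and within-child CV of 5–15%, about 4 to 36 of 50 children with unchanged kidney function would be flagged at least once, against about 0 to 19 without growth. The excess comes from growth and variability acting together. No test, sample size or visit is affected; what suffers is the reading of one row in a single-arm safety table. The change is worth making because it is cheap and uses data already scheduled.

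**What to change.** In the creatinine row of Table 11-4:

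1. Replace the adult limit with the number and percentage of subjects with Bedside Schwartz eGFR <60 mL/min/1.73 m², the protocol's own screening equation and value, calculated from same-visit creatinine and length/height.
2. Reword the two relative criteria as ≥30% increase and ≥100% increase from baseline, and keep both.
3. Beside the ≥30% row, add a count of the same size on length-adjusted creatinine: eGFR ≤ baseline/1.3. Comparing the two counts shows how much of the ≥30% row goes with growth.

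A ≥30% fall in eGFR should not stand in for item 3. It needs length-adjusted creatinine to rise by 1/0.7 = 1.43 times, or 43%, which would quietly loosen the criterion.

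The cost is an edit to one SAP table and one derived variable. Length/height is already scheduled at every clinic visit with chemistry; a rule is needed for unscheduled draws without a length. The row will differ from any standard table that the sponsor uses across studies. The adjusted count removes the growth part but not measurement noise: for 50 children on the 8-draw schedule with unchanged kidney function, about 0, 8 and 19 would still be flagged at CV 5, 10 and 15%.
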